Follow-up period is the on-study time period after the EOT Visit. All patients that discontinue study drug and have not withdrawn full consent to participate in the study will continue in the follow-up phase for survival and initiation anticancer therapy. Follow up will continue approximately every 12 weeks (+/- 3 weeks), until death, withdrawal of consent, or the study closes, whichever is the earliest. This evaluation may be made by record review and/or telephone contact.

Study Treatment

Patients will receive nivolumab 3 mg/kg as IV infusion over 30 min every 3 weeks (Day 1 of every 21-day cycle), followed by escalating doses of ABI-009 30, 45, 75 mg/m² for 2 of every 3 weeks by IV infusion over 30 minutes. ABI-009 dosing will start after 2nd nivolumab dose and to be administered on Day 8 and Day 15 of every cycle beginning in Cycle 2. Patients will continue therapy until unequivocal clinical disease progression, unacceptable toxicity, or until in the opinion of the investigator the patient is no longer benefiting from therapy, or at the patient's discretion.

Overview of Key Safety Assessments

Safety and tolerability will be monitored through continuous reporting of treatment-emergent and treatment-related adverse events (AEs), AEs of special interest, laboratory abnormalities, and incidence of patients experiencing dose modifications, dose delay/dose not given, dose interruptions, and/or premature discontinuation of IP due to an AE. All AEs will be recorded by the investigator from the time the patient signs informed consent until 28 days after the last dose of IP. Adverse events will be graded by National Cancer Institute (NCI) Common Terminology Criteria for Adverse Events (CTCAE) v4.03.

Physical examination, vital signs, laboratory assessments (e.g., serum chemistry, hematology), and ECOG performance status will be monitored. All SAEs (regardless of relationship to IP) will be followed until resolution. Local laboratory analysis will be performed as per study schedule.

The MTD for ABI-009 will be determined, and will be used in the Phase 2 part of the study.

Overview of Key Efficacy Assessments

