In Trial 1, where patients were evaluated at baseline and during the trial for thyroid function, Grade 1 or 2 hypothyroidism occurred in 8% (21/268) of patients receiving nivolumab and none of the 102 patients receiving chemotherapy. The median time to onset was 2.5 months (range: 24 days-11.7 months). Seventeen of the 21 patients with hypothyroidism received levothyroxine. Fifteen of 17 patients received subsequent nivolumab dosing while continuing to receive levothyroxine.

Grade 1 or 2 hyperthyroidism occurred in 3% (8/268) of patients receiving nivolumab and 1% (1/102) of patients receiving chemotherapy. The median time to onset in nivolumab-treated patients was 1.6 months (range: 0-3.3 months). Four of five patients with Grade 1 hyperthyroidism and two of three patients with Grade 2 hyperthyroidism had documented resolution of hyperthyroidism; all three patients received medical management for Grade 2 hyperthyroidism.

- **Any other severe or Grade 3 treatment-related adverse reactions**

Other clinically significant immune-mediated adverse reactions can occur. Immune-mediated adverse reactions may occur after discontinuation of nivolumab therapy.

The following clinically significant, immune-mediated adverse reactions occurred in less than 1% of nivolumab-treated patients in Trial 1: pancreatitis, uveitis, demyelination, autoimmune neuropathy, adrenal insufficiency, and facial and abducens nerve paresis.

Across clinical trials of nivolumab administered at doses of 3 mg/kg and 10 mg/kg the following additional clinically significant, immune-mediated adverse reactions were identified: hypophysitis, diabetic ketoacidosis, hypopituitarism, Guillain-Barré syndrome, and myasthenic syndrome.

Nivolumab was discontinued for adverse reactions in 9% of patients. Twenty-six percent of patients receiving nivolumab had a drug delay for an adverse reaction. Serious adverse reactions occurred in 41% of patients receiving nivolumab. Grade 3 and 4 adverse reactions occurred in 42% of patients receiving nivolumab. The most frequent Grade 3 and 4 adverse reactions reported in 2% to less than 5% of patients receiving nivolumab were abdominal pain, hyponatremia, increased aspartate aminotransferase, and increased lipase. Other adverse events that occurred in $\geq 10\%$ of patients were rash, pruritus, cough, upper respiratory tract infection, peripheral edema, increased AST, increased alkaline phosphatase, hyponatremia, increased ALT, and hyperkalemia, with

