1.4. Rationale for the Schedule of the Study

In this study nivolumab will be given once every 3 weeks (D1 of a 3 week cycle) and ABI-009 will be administered on D8 and D15 of the 3 week cycle starting in Cycle 2 (C2). Thus, ABI-009 will be given weekly for 2 weeks with a 1 week break.

Although nivolumab is approved on a biweekly schedule, in this study, because nivolumab is being given in combination with ABI-009 which is administered 2 out of 3 weeks, a 3 weekly schedule for nivolumab was adopted. In a prior Phase 3 combination study with ipilimumab, nivolumab 3 mg/kg was given every 3 weeks during the time when combination therapy was given (65). In this study, nivolumab and ABI-009 have different mechanisms of action. Therefore, it is not expected that the individual toxicities would significantly overlap. As a safety precaution, nivolumab will be given every three weeks (instead of every 2 weeks) when used in combination with ABI-009. Additionally, escalating doses of ABI-009 will start two dose levels below the MTD of 100 mg/m² observed in the Phase 1 study (44), as well as a de-escalation schedule if DLT is noted at Dose Level 1 (See Dose Reduction in [Section 6](#)).

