2.3. Study Design

This is an open label, dose-seeking phase 1/2 study using a defined dose of nivolumab and escalating doses of ABI-009 given intravenously.

I. Dose Escalation Phase 1 Part of Study: The study will employ the standard "cohort of three" design (Storer, 1989). Three patients are treated at each dose level with expansion to six patients per cohort if DLT is observed in one of the three initially-enrolled patients at each dose level. If no DLT occurs after 2 doses, escalation to the next dose level will be permitted. The maximum tolerated dose is defined as the highest safely tolerated dose, where not more than one patient experienced DLT, with the next higher dose level having at least two patients who experienced DLT. Patients in the dose escalation study may continue treatment at their designated dose levels up to eighteen 3-week treatment cycles or until significant disease progression or unacceptable toxicity occurs. No intra-patient dose escalation will take place.

Dose of nivolumab: 3 mg/kg IV over 30 min. q 3 weeks

NB: ABI-009 will start after 2nd Nivo dose, and will be administered on D8 and D15 beginning in C2.

Dose of ABI-009: Escalating doses IV over 30 min for 2 of every 3 weeks:

Treatment Cycle	# Pts.	Dose Level	Dose, mg/m2
Every 3 weeks	3-6	I	56
Every 3 weeks	3-6	II	75
Every 3 weeks	3-6	III	100

Note: DLT includes any \geq Grade 3 colitis, hepatitis, or pneumonitis, any Grade 1-2 colitis, hepatitis or pneumonitis that recurs, worsens or persists with oral steroids longer than 14 days, symptoms of adrenal crisis, any Grade 4 hematologic toxicity or any \geq Grade 3 non-hematologic toxicity.

II. Expansion Phase 2 Part of Study: Following dose escalation, an additional 22-28 patients will receive ABI-009 at the MTD and defined doses of nivolumab to assess overall safety and potential efficacy in a greater number of patients. Patients in the expansion

phase of the study may continue treatment up to 18 3-week treatment cycles or until significant disease progression or unacceptable toxicity occurs.

The study will be conducted in compliance with International Conference on Harmonisation (ICH) Good Clinical Practices (GCPs).

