3. STUDY POPULATION

3.1. Number of Patients

The anticipated enrollment into this study will be approximately 12-18 patients for the Phase 1 part of the study and approximately 22-28 evaluable patients for the Phase 2 part of the study. The rationale for the number of patients is detailed in [Section 8](#).

The investigator will be expected to maintain a screening log of all potential study candidates that includes limited information about the potential candidate, date, and outcome of the screening process (e.g., enrolled into study, reason for ineligibility, or refused to participate).

Before any study-specific procedure, the appropriate written informed consent must be obtained (see [Section 11.5](#)).

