6. DESCRIPTION OF STUDY TREATMENTS (ABI-009/NIVO)

6.1. ABI-009/Nivolumab Dosage, Administration, and Schedule

For the Phase 1 part of study, patients will receive nivolumab 3 mg/kg as IV infusion over 60 min every 3 weeks, followed by escalating doses of ABI-009 56, 75, 100 mg/m² for 2 of every 3 weeks by IV infusion over 30 minutes. ABI-009 will start on Day 8 of Cycle 2. If DLT develops in more than 1 patient at Dose 56 mg/m², the dose will be de-escalated to 45 mg/m² and to 30 mg/m² if DLT develops at 45 mg/m². Patients will continue therapy until unequivocal clinical disease progression, unacceptable toxicity, or until in the opinion of the investigator the patient is no longer benefiting from therapy, or at the patient's discretion.

For the Phase 2 part of study, patients will receive nivolumab 3 mg/kg as IV infusion over 30 min every 3 weeks, followed by ABI-009 at the MTD dose for 2 of every 3 weeks by IV infusion over 30 minutes. ABI-009 will start on Day 8 of Cycle 2. Patients will continue therapy until unequivocal clinical disease progression, unacceptable toxicity, or until in the opinion of the investigator the patient is no longer benefiting from therapy, or at the patient's discretion.

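### The MTD definition needs a failed level above, but the ladder ends at 100 mg/m²: if that level clears, no dose qualifies, and any level can be declared on 0/3

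*Combined protocol and SAP*

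**What the plan says.** The MTD is the sole primary endpoint (Sections 2.2.1 and 8.1). Section 2.3 and the Synopsis (Study Design) define it by two joined conditions. The dose must be the highest one tolerated, with no more than one patient with DLT. The second condition is "with the next higher dose level having at least two patients who experienced DLT".

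Section 6.1 gives the ladder as "escalating doses of ABI-009 56, 75, 100 mg/m² for 2 of every 3 weeks", and the dose tables in Section 2.3 and the Synopsis agree. The only other levels go down, to 45 and 30 mg/m². Section 1.4 explains the top of the ladder: "escalating doses of ABI-009 will start two dose levels below the MTD of 100 mg/m² observed in the Phase 1 study". The Synopsis paragraph on Study Treatment conflicts with all of these and lists 30, 45 and 75 mg/m².

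A level starts with three patients, with "expansion to six patients per cohort if DLT is observed in one of the three initially-enrolled patients". No sentence requires six patients at the dose finally declared. Section 3.1 expects "approximately 12-18 patients for the Phase 1 part of the study".

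Phase 2 depends on the result. Section 2.3 states that "an additional 22-28 patients will receive ABI-009 at the MTD and defined doses of nivolumab", and the Synopsis (Overview of Key Safety Assessments) says: "The MTD for ABI-009 will be determined, and will be used in the Phase 2 part of the study".

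**The concern.** Suppose 56, 75 and 100 mg/m² all clear. Then 56 and 75 fail the second condition, because the level above each was tolerated, and 100 cannot satisfy it, because there is no level above. The plan has no outcome of MTD not reached, no maximum administered dose, and no rule for a recommended Phase 2 dose. Followed literally, it returns no value for the primary endpoint and no dose for the 22-28 Phase 2 patients. Calling 100 mg/m² the MTD would report a toxicity ceiling that the trial had not observed.

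The second problem is separate. Because a cohort expands only after a DLT, the declared dose can rest on three patients. This can happen at 75 mg/m² as well as at 100, so it is not confined to the top of the ladder.

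**Working it through.** **Inputs.** The cohort rule, MTD definition and ladder come from Section 2.3, and Table 1 from Section 8.2. The DLT rates by dose are assumptions. Write p for the true DLT rate at a level and q = 1 − p.

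**1. Reproduce Table 1.** A level clears on 0/3, or on 1/3 followed by 0/3: P(clear) = q³ + 3pq² × q³ = q³ + 3pq⁵. The plan's figures are 0.91, 0.71, 0.49, 0.31 and 0.17, and all five reproduce.

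| p | P(clear) | on 0/3 (q³) | share of clears on 0/3 | at most 1/6 (q⁶ + 6pq⁵) |
|---|---|---|---|---|
| 10% | 0.9061 | 0.729 | 0.805 | 0.8857 |
| 20% | 0.7086 | 0.512 | 0.723 | 0.6554 |
| 30% | 0.4943 | 0.343 | 0.694 | 0.4202 |
| 40% | 0.3093 | 0.216 | 0.698 | 0.2333 |
| 50% | 0.1719 | 0.125 | 0.727 | 0.1094 |

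**2. How often no dose meets the definition.** This is the product of P(clear) over 56, 75 and 100 mg/m². For 10/20/30% it is 0.9061 × 0.7086 × 0.4943 = 0.317.

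**3. How often filling 100 mg/m² to six changes the outcome.** This is P(reach 100) × [P(clear) − P(at most 1/6)] at 100. For 10/20/30%: 0.9061 × 0.7086 = 0.642; 0.4943 − 0.4202 = 0.0741; product 0.048.

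| DLT rates at 56/75/100 | all three clear | reach 100 | difference at 100 | outcome changed |
|---|---|---|---|---|
| 10/10/10% | 0.744 | 0.821 | 0.0204 | 0.017 |
| 10/10/20% | 0.582 | 0.821 | 0.0532 | 0.044 |
| 10/20/30% | 0.317 | 0.642 | 0.0741 | 0.048 |
| 20/30/40% | 0.108 | 0.350 | 0.0760 | 0.027 |
| 30/40/50% | 0.026 | 0.153 | 0.0625 | 0.010 |

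**4. Where a declaration on 0/3 arises.** At 75 mg/m² it needs 56 to clear, 75 to clear on 0/3, and 100 to fail. For 10/20/30%: 0.9061 × 0.512 × (1 − 0.4943) = 0.23. For 20/30/40%: 0.7086 × 0.343 × 0.6907 = 0.17. For 30/40/50%: 0.4943 × 0.216 × 0.8281 = 0.09. The matching chances that 100 mg/m² clears on 0/3 are 0.642 × 0.343 = 0.22, 0.350 × 0.216 = 0.08 and 0.153 × 0.125 = 0.02. A rule that filled only 100 mg/m² would therefore miss much of the problem.

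**5. What the data would support.** One-sided 95% exact upper bounds on the DLT rate are 1 − 0.05^(1/3) = 63% for 0/3, 1 − 0.05^(1/6) = 39% for 0/6, and 58% for 1/6 (Clopper-Pearson).

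**6. Phase 1 size.** If every level clears on 0/3, the written rule ends at 3 + 3 + 3 = 9 patients, below the stated minimum of 12. Six at the last level gives 3 + 3 + 6 = 12.

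**The case against.** The strongest reply is that the gap concerns a label. The definition opens by asking for the highest tolerated dose, and Section 1.4 ties the top of the ladder to the earlier single-agent MTD, so the sponsor would almost certainly take 100 mg/m² forward. Analyses are descriptive (Sections 8.6 and 8.8.1) and DLTs are tabulated by dose level (Section 8.2), so a reader would see what happened. That stands, and it limits the weight of the point. It does not close the gap: choosing 100 mg/m² drops the second condition, and no text permits that.

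On 0/3, the plan chose a standard design and states its operating characteristics correctly. The Phase 1 minimum of 12 suggests that six at the final level was intended. Seven patients received 100 mg/m² as a single agent in the earlier trial (Section 1.2.4), although weekly for three of four weeks and without nivolumab. Phase 2 has holds, reductions and discontinuation rules (Section 6.2.1), although the reduction steps are written out only from 56 mg/m² and no DLT rule revises the Phase 2 dose. Accepting 1/6 gives a bound (58%) little better than 0/3 (63%). These points stand. The two problems also seldom matter together: the undefined path is common when DLT rates are low, where filling 100 mg/m² matters least.

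A reader might infer from "Grade 3 and 4 adverse reactions occurred in 42% of patients receiving nivolumab" that the high assumed DLT rates are the likely ones. Section 1.3.3 does not support that. The figure comes from nivolumab alone, given every two weeks over a median exposure of 5.3 months, and it is not a DLT rate. It shows only that high rates cannot be ruled out.

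**Conclusion.** The point holds, with modest weight. If 100 mg/m² clears, the written definition gives no MTD and no rule sets the Phase 2 dose. Over the assumed rates this has probability 0.03 to 0.74, a range that is wide because the documents contain no DLT rates for the combination. The effect is on how the primary result is reported and on the safety basis for opening Phase 2. No hypothesis test depends on it.

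Separately, any level can be declared on three patients; at true rates of 10-50%, about 69-81% of clears at a level rest on 0/3.

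Two stronger readings should be avoided. One is that the trial would have no usable Phase 2 dose: the opening of the definition and Section 1.4 both point to 100 mg/m². The other is that a six-patient rule would greatly change which dose is chosen: filling 100 mg/m² alters the outcome in about 1-5% of trials under the assumed rates.

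**What to change.** After the MTD definition in Section 2.3 and in the Synopsis (Study Design), add:

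*Before Phase 2 opens, the dose to be declared will be filled to six patients and accepted if no more than 1 of 6 has a DLT; if two or more have a DLT, the next lower level is filled to six and assessed in the same way. If 100 mg/m² is accepted, the MTD is reported as not reached (maximum administered dose 100 mg/m²) and 100 mg/m² is the Phase 2 dose.*

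Correct the dose list in the Synopsis (Study Treatment) to 56, 75 and 100 mg/m². Table 1 describes escalation from a single level and stays as it is.

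**Cost.** Usually 0-3 extra Phase 1 patients, within the planned 3-6 per level. Six at each of the three levels gives 3 × 6 = 18, the stated maximum; only a fill that fails at 56 mg/m² and leads down to 45 could exceed it. Each fill may delay Phase 2 by up to about three months. At 40-50 patients over 24 months (1.7-2.1 a month), three patients take 1.4-1.8 months; two 21-day cycles add six weeks if DLTs are observed to the end of Cycle 2. That window is an assumption, because the plan speaks only of two doses.

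**Gain.** Chiefly a primary endpoint and a Phase 2 dose that are defined on every path, and settled before the data are seen.

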- Local Laboratory Assessments: chemistry, complete blood count (CBC), differential, platelet count, coagulation, urinalysis, thyroid function, pregnancy

test (women of child-bearing potential, includes tubal ligations), HIV, hepatitis B surface antigen, hepatitis C antibody, fasting lipids

- Urinalysis (a urine dipstick may be used)
- CT or MRI, must be performed within 2 weeks prior to study day 1, preferably as close to the day of enrollment as possible
- Immunohistochemistry for PTEN mutation on patient's archived tumor

A patient is considered enrolled when the investigator decides that the patient has met all eligibility criteria. The investigator is to document this decision and date, in the patient's medical record and in/on the electronic case report form (CRF).

All screening tests and procedures must be performed within 14 days of study day 1, unless specified otherwise in the study procedures listed in [Section 4](#).

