6.2. ABI-009 Dose Modification and Stopping Rules

6.2.1. Dosage Adjustments, Delays, Rules for Withholding or Restarting, Permanent Discontinuation

If, treatment cannot be administered on the planned visit date, ABI-009 may be administered +/- 2 days from the scheduled date. Prior to ABI-009 administration on Day 1 of each cycle, patients must meet the following hematological requirements:

- ANC $\geq 1.5 \times 10^9/L$
- Platelet count $\geq 100 \times 10^9/L$
- Hemoglobin $\geq 9 \text{ g/dL}$

The treatment will be on hold up to 14 days until the patient has fulfilled these criteria.

If a Grade 4 hematologic toxicity occurs, the dose of ABI-009 is held until toxicity resolves to Grade 1 or less. The dose of ABI-009 is then modified according to the dose modification section. If a Grade 3 non-hematologic toxicity occurs, both nivolumab and ABI-009 are withheld until toxicity resolves to Grade 1 or less. The dose of ABI-009 is then modified according to the dose modification section. Nivolumab has no dose modification.

The maximum delay between a missed scheduled dose and the next one (whichever dose was missed) should not be longer than 14 days. Approval from the Medical Monitor is required to restart study treatment after ≥ 21 days of interruption.

During the Phase 2 part of the study, doses of ABI-009 will be reduced for hematologic and other toxicities. Two levels of dose modifications are permitted according to the criteria below. If MTD is determined to be 56 mg/m², dose reductions will occur sequentially (45 mg/m² and 30 mg/m²), there should be no direct reduction by two dose

levels. If a toxicity requiring dose modification occurs following the second dose reduction of ABI-009, further treatment should be discontinued. Dose adjustments are to be made according to the system showing the greatest degree of toxicity. Toxicities will be graded using the NCI CTCAE Version 4.03.

Guidelines for dose modifications and interruptions for management of common toxicities associated with the study treatment(s) are provided in this section:

- General guidelines for clinically significant toxicities related to study treatment

And

- Specific guidelines for adverse events of special interest, which are events that have been observed with higher frequency or severity.

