Respiratory events	Pneumonitis, bronchiolitis obliterans, and/or organizing pneumonia	Grade 2	Hold ABI-009 immediately for up to 3 weeks until resolved to ≤ grade 1, then reduce by 1 dose level. If it is still a Grade 2 after 3 weeks, discontinue treatment. If > Grade 2 recurs after resuming ABI-009 at a reduced dose level, discontinue treatment
		Grade ≥3	Permanently remove patient from protocol treatment

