6.2.2.2. Criteria for Conditional Withholding of ABI-009 Due to Potential Hepatotoxicity

For patients who do not meet the criteria for permanent discontinuation of ABI-009 and have no underlying liver disease, and eligibility criteria requiring normal transaminases and TBL at baseline or patients with underlying liver disease and baseline abnormal transaminases, the following rules are recommended for withholding of ABI-009:

- Elevation of either AST or ALT according to the following schedule:

Baseline AST or ALT value	AST or ALT elevation
Any	> 8x ULN at any time
Any	> 5x ULN but < 8x ULN for \geq 2 weeks
Any	> 5x ULN but < 8x ULN and unable to adhere to enhanced monitoring schedule
Any	\geq 3x ULN with clinical signs or symptoms that are consistent with hepatitis (such as right upper quadrant pain/tenderness, fever, nausea, vomiting, jaundice).

- OR: TBL $>$ 3x ULN at any time
- OR: ALP $>$ 8x ULN at any time

ABI-009 should be withheld pending investigation into alternative causes of DILI. Rechallenge may be considered if an alternative cause for impaired liver tests (ALT, AST, and ALP) and/or elevated TBL is discovered and the laboratory abnormalities resolve to normal or baseline.

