8.3. Efficacy Analysis

The Efficacy Analysis Dataset includes all enrolled patients with measurable tumor per RECIST v1.1 at baseline who receive at least two doses of ABI-009 and had a follow-up CT scan/MRI.

The disease control rate (DCR; CR+PR+SD), objective response rate (ORR; CR + PR), progression free survival (PFS), recurrence-free survival (RFS) will be assessed by an local radiologic assessment using Response Evaluation Criteria in Solid Tumors (RECIST) v1.1.

The focus of the study is to estimate the DCR in patients treated with ABI-009 and nivolumab. Patients who progress before receiving ABI-009 will be replaced, and will not be included in the statistical analysis. The number and percentage of patients achieving disease control (CR, PR or SD) will be summarized.

Analysis of other efficacy endpoints, PFS at 4 months, RFS at 4 months, median PFS, median RFS and median OS will be assessed for all subtypes together, and separately in the five sarcoma subtypes with metastatic disease and locally advanced disease. Patients may be stratified further as locally advanced or metastatic. Patients in the locally advanced tumor subgroup may be clinically indicated to receive surgery if there is sufficient tumor shrinkage, which could introduce a bias in the assessment of the PFS at 4 months, median PFS, and OS. Recurrence-free survival (RFS) defined as progression free survival + absence of disease progression or recurrence after surgical resection has been added to the secondary endpoints to obviate this bias.

PFS, RFS and OS will be summarized using Kaplan-Meier (KM) analysis. The number of patients in each category is expected to be small; therefore, PFS at 4 months, RFS at 4 months, median PFS, and median OS for these patients will be summarized by descriptive statistics.

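### Escalation after two doses can precede the date on which the 14-day steroid DLT criterion can be scored, and the nivolumab lead-in does not protect a patient who is already in it

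*Combined protocol and SAP*

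**What the plan says.** The Synopsis (Study Design) and Section 2.3 give the same escalation rule: "If no DLT occurs after 2 doses, escalation to the next dose level will be permitted". Neither sets a DLT observation window in days or cycles, and neither says which drug's doses are counted. I read them as ABI-009 doses.

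The DLT note in the same places includes "any Grade 1-2 colitis, hepatitis or pneumonitis that recurs, worsens or persists with oral steroids longer than 14 days".

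Section 6.1 states that "ABI-009 will start on Day 8 of Cycle 2", so every patient first has two nivolumab doses at a dose that is the same at all levels. Section 5.1 defines entry by eligibility alone: "A patient is considered enrolled when the investigator decides that the patient has met all eligibility criteria". No section says when a dose level is assigned, or whether nivolumab may start before that level is open.

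The hold rules in Sections 6.2 and 6.3 act on the patient who has the event. For Grade 2 pneumonitis, for example, Table 5 says "Hold ABI-009 immediately for up to 3 weeks until resolved". None of them holds the next cohort's dose, and no cohort safety review is described.

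**The concern.** The decision to escalate can be taken while a steroid-treated Grade 1-2 event at the lower level is still undetermined as a DLT. A next-level patient already on nivolumab could then receive 75 or 100 mg/m² when the lower level may turn out to have had a DLT and to have needed six patients first. The site would have to settle afterwards whether to pause the higher level while it fills the lower one. This touches patient exposure and the MTD, which is the primary endpoint.

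Only the persistence part of the criterion takes 14 days to read. Recurrence or worsening can be scored earlier. Section 6.3.1 directs steroids from Grade 2 for these three conditions, so in practice the issue is mostly about Grade 2 events.

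**Working it through.** **Plan's own figure.** Table 1 follows from the 3+3 rule, P(escalate) = (1-p)³ + 3p(1-p)²·(1-p)³. At p = 10, 20, 30, 40 and 50% this gives 0.906, 0.709, 0.494, 0.309 and 0.172, which match the printed 0.91, 0.71, 0.49, 0.31 and 0.17. The table takes every DLT as scored before the decision.

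**Calendar** (Sections 2.3 and 6.1, 21-day cycles). Study day = (cycle - 1) × 21 + day, on the clock of the last lower-level patient.

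- First ABI-009 dose, C2D8: 21 + 8 = 29. Second, C2D15: 21 + 15 = 36. This is the earliest decision day.
- Lead-in from C1D1 to C2D8: 29 - 1 = 28 days.
- C3D8: 42 + 8 = 50. C3D15: 42 + 15 = 57. Visits may move by 2 days (Table 2).

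**When the criterion can first be scored.** Scoring day = steroid start + 15, the first day on which more than 14 days have elapsed. Counting steroid days inclusively makes it one day earlier.

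- Steroids from day 36: 36 + 15 = 51.
- Grade 2 colitis with onset on day 36. Section 6.3.1 starts steroids only after more than 5 days, so from about day 41: 41 + 15 = 56.
- Events after the first ABI-009 dose are mostly caught, because Table 5 holds the second dose for Grade 2 pneumonitis and Grade 2 diarrhea, and so delays the decision. The exception is Grade 2 hepatitis without symptoms (AST/ALT 3-5 × ULN). Section 6.2.2.2 withholds at that range only for "3x ULN with clinical signs or symptoms that are consistent with hepatitis". With steroids from day 29 it is scorable on 29 + 15 = 44.

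**Patient who starts nivolumab on the decision day.** First higher dose: 36 + 28 = 64, or 62 with the visit window. Slack: 64 - 51 = 13 days (11 with the window), or 64 - 56 = 8 days (6) for the colitis case. This patient is not at risk.

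**Patient already in the lead-in.** Let s be this patient's C1D1 on the lower-level clock. The gap applies if 36 ≤ s + 28 < scoring day.

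- Scoring day 51: s = 8 to 22, which is 14 to 28 days before the decision (15 start days).
- Scoring day 56: s = 8 to 27, which is 9 to 28 days before (20 start days).

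**How many patients fall in the window.** This assumes that accrual runs without pause at the planned average, 40-50 patients (Synopsis) in about 24 months (Section 2.4), or 730 days.

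- 15 days: 40 × 15/730 = 0.82 to 50 × 15/730 = 1.03 patients per escalation step.
- 20 days: 40 × 20/730 = 1.10 to 50 × 20/730 = 1.37.
- If no lead-in starts before the decision: 0.

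These count patients in a calendar window, not patients affected. A qualifying event must also be open at the lower level.

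**How often an event might be open.** Section 1.3.3 reports Grade 2 immune-mediated events in Trial 1 as 5 pneumonitis, 1 colitis and 1 hepatitis among 268 patients: 7/268 = 2.6%. For a cohort of three, 1 - (1 - 7/268)³ = 7.6% over the whole exposure, before requiring onset near day 36 and persistence beyond 14 days. Onset was a median of 2.2 months (from 25 days) for pneumonitis, 2.5 months (from 1 month) for colitis, and 86-113 days for hepatitis. All this is nivolumab alone. Section 1.2.1 cites pneumonitis in 8% with rapamycin and rapalogs, so the combination could be higher.

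**The case against.** The strongest reply is that the exposed practice is inferred. Section 2.3 speaks of patients initially enrolled at each level and of designated levels, which can naturally be read as entry to a level already open. Escalation is permitted, not required. At a single centre, the team treating the lower-level patient also decides the next dose. Dexamethasone is given on D8 from Cycle 2 to reduce pneumonitis and hepatitis (Section 7.6), and the general rule in Section 6.2.1 allows withholding for any clinically significant event. All of this stands, and it keeps the priority low. It does not remove the gap, because no sentence bars an early lead-in or makes the next level wait.

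Three stronger readings are tempting and should not be taken from this point.

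- *Every next-level patient is exposed.* Not so. The 28-day lead-in outlasts the scoring date for anyone who starts nivolumab on or after the decision.
- *A late DLT is lost from the MTD.* Not on the text. The expansion and MTD rules carry no time limit, so a late DLT counts. Patients may continue at their designated level, and Section 10.3 allows withdrawal from treatment at any time. What is unstated is whether the higher level pauses meanwhile.
- *Table 1 overstates safety by a known amount.* The documents do not give the share of DLTs still unscored at the decision, so no effect on escalation probability is claimed.

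**Conclusion.** Two rules in the plan are out of step: escalation can be permitted on day 36, while one DLT criterion may not be readable until about day 51, or day 56 for late-treated Grade 2 colitis. The lead-in closes this for patients who start nivolumab on or after the decision. It leaves it open for a patient already in the lead-in.

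The conclusion assumes that the two doses are ABI-009 doses, that the decision is taken as early as day 36, and that the site starts lead-in before the decision. The plan is silent on the last of these. A decision taken on or after the scoring day has no gap. Under the accrual assumption about one patient per step would be in the window. The chance that an event is open at the same time is not given and is probably small. The change is cheap and concerns dose exposure, so it is worth making, but its priority is optional to advisable.

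**What to change.** In the Synopsis and Section 2.3, state the following.

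1. Escalation is permitted only when no DLT has occurred after two ABI-009 doses, and every steroid-treated Grade 1-2 colitis, hepatitis or pneumonitis in the deciding cohort with onset on or before the day of the second ABI-009 dose has resolved or been scored. Scoring requires more than 14 days of steroids (about day 51, or day 56 for late-treated colitis), confirmed by an adverse event check on or after that day. C3D8 on its nominal day 50, or day 48 if held early, is too soon.
2. Until then no patient receives a first ABI-009 dose at the next level. A waiting patient stays on nivolumab and starts ABI-009 at the next D8. This planned wait is exempt from the Section 6.2.1 limit, "The maximum delay between a missed scheduled dose and the next one (whichever dose was missed) should not be longer than 14 days", and from its approval step for interruptions of 21 days or more.
3. Events with later onset do not hold dosing. If scored as DLTs, they count at the level where they arose and trigger its expansion rule, and no new patient starts the higher level until this is settled.

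The onset cut-off is needed. Without it, steroids started on day 50 would be scorable only on day 65 and would hold even a patient who started nivolumab on the decision day (first dose day 64). Item 3 mainly makes explicit what the untimed rules already imply.

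Cost: nothing when no such event is open, or when next-level patients start nivolumab on or after the decision. Otherwise a waiting patient's first ABI-009 dose moves one cycle, 21 days. The earliest such dose moves from day 36 to 36 + 21 = 57, past both scoring days if steroids start as Section 6.3.1 directs. That patient spends longer on nivolumab alone and, on progression, falls under the existing rule: "Patients who progress before receiving ABI-009 will be replaced, and will not be included in the statistical analysis". For the ordinary case C3D15 (day 57 ± 2) can serve as the check. For late-treated colitis it must fall on day 56 or later.
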